4.1 Schedules of Assessments (SoA)

Table 1: Schedule of Assessments (Part 1a)

	Screening		Treatment			Outpatient Visits (Cohorts 4 and 5 only)		Follow-Up ¹
	D-28 to -2	D-1	D1	D2	D3 (Discharge ² or early termination)	D4	D5	D8 (between Days 8 and 11)
Informed consent	X							
Height and BMI	X							
Weight	X	X			X			
Inclusion/Exclusion Criteria	X	X ³	X					
Demographics ⁴	X							
Medical History		X						
Concomitant Medications						Continuously		
Physical and Neurological Examination	X	X			X			X
Vital Signs including orthostatic vital signs, 12-lead ECG, Body Temperature ⁵	X	X	X	X	X			X
12-Lead Telemetry ⁶			X	X	X			
Hematology, Clinical Chemistry, HbA1c, and Urinalysis ⁷	X	X	X	X	X			X
Thyroid Panel	X	X			X			X
Coagulation Tests	X	X			X			
Drug Screening, Alcohol Breath, and Urine Cotinine Test	X	X						
COVID-19 PCR	X	X						
Virus Serology	X							
Study Drug Administration			X					
PK Blood Sampling ⁸			X	X	X	X	X	
PK Urine Sampling ⁹			X	X	X			
FSH Test in Post-Menopausal Participants ¹⁰	X							
Pregnancy Test ¹¹	X	X			X			
C-SSRS	X	X						X
Adverse Events						Continuously		
Outpatient Visits	X					X	X	X
Residence in Clinic				X				

D=day; ECG=electrocardiogram; PK=pharmacokinetic

1. Follow-up examination will take place on Day 8 (or between Day 8 and 11).
2. Discharge after completion of all study 48-hour assessments.
3. Continuous eligibility assessments on Day -1 including continuous medical history on Day -1 and prior to dosing on Day 1.
4. Including sex, date of birth, race, and ethnicity.
5. Will be performed at Screening, at admission on Day -1, Day 1 pre-dose (up to 60 min pre-dose), and 1 (± 20 min), 2 (± 20 min), 4 (± 20 min), 8 (± 60 min), 12 (± 60 min), and 16 (± 60 min) hours post-dose, at Day 2 (24 and 36 [± 60 min] hours post-dose), on Day 3 (48 [± 60 min] hours post-dose), and at Follow-up. Orthostatic vital signs will be measured at Screening and at admission on Day -1 only.
6. Will be started approximately 1-2 hours pre-dose at Day 1 and will be continued to approximately 48 hours post-dose.
7. Will take place at Screening (in fasted state, i.e., participants should fast for 4 hours prior to sample collection), at Day -1 (in fasted state), Day 1 at 8 hours post-dose (in not-fasted state), at Day 2 (in fasted state), at Day 3 (in fasted state), and at Follow-up (in fasted state). HbA1c will be performed at Screening.

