Participants will be admitted to the clinical unit on the day before study drug administration (Day -1) for baseline assessments, and to confirm eligibility. Participants will be dosed in the fasted state and will be required to fast for a minimum of 10 hours prior to dosing and 4 hours following dosing. Except for water given with the study drug, no fluids will be allowed from 1 hour before dosing until 1 hour after dosing. Participants in Study Part 1a will stay in the clinical unit for 4 days (3 nights), from Day -1 until Day 3. Blood samples for PK analysis for Cohorts 1, 2, and 3 will be collected pre-dose and at specified time points up to Day 3 (48 hours) post-dose and blood samples for PK analysis for Cohorts 4 and 5 will be collected pre-dose and at specified time points up to Day 5 (96 hours) post-dose. Urine samples for PK analysis will be collected from pre-dose and during specified time intervals up to Day 3 (48 hours post-dose). PK blood samples for Cohorts 4 and 5 will be collected at outpatient visits on Day 4 (72 hours post-dose) and Day 5 (96 hours post-dose). All participants in each cohort will return for a follow-up visit on Day 8 (between Day 8 and Day 11).

Physical and neurological examinations, safety labs (including drug screen, cotinine test, and alcohol breath test), vital signs, ECG, and telemetry will be performed at specified time points. AEs will be recorded throughout the study. For details regarding the timing of specific procedures, see [Table 1](#).

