11.7.1 Time Period and Frequency for Collecting AE and SAE Information

All AEs will be collected continuously from time of informed consent until the Follow-up Visit ([Section 4.1](#)).

Medical occurrences that begin after obtaining informed consent will be recorded as AEs.

All SAEs will be recorded and reported to the Sponsor or designee immediately and under no circumstance should this exceed 24 hours, as indicated in [Section 13.3](#). The Investigator will submit any updated SAE data to the Sponsor within 24 hours of it being available.

Investigators are not obligated to actively seek information on new AEs or SAEs after conclusion of the study participation. However, if the Investigator learns of any SAE, including a death, at any time after a participant has been discharged from the study, and the Investigator considers the event to be reasonably related to the study treatment or study participation, the Investigator must promptly notify the Sponsor.

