11.7.2 Method of Detecting AEs and SAEs

Care will be taken not to introduce bias when detecting AEs and/or SAEs. Open-ended and nonleading verbal questioning of the participant is the preferred method to inquire about AE occurrences.

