6.1 General Methods

SAS for Windows software will be used to perform all statistical analyses. All relevant data in the database will be presented in the data listings. Unless otherwise stated, all listings will be sorted by study part, treatment, participant number, and assessment date/time. For the purposes of the summary tables, all participants randomized to placebo will be pooled into a single placebo group (i.e., All placebo). Unless otherwise stated, there will also be an overall section for all ATH-399A doses combined (i.e., All ATH-399A). All summaries will be presented separately for each study part. Unless otherwise stated, the descriptions of the analyses which follow apply to all study parts.

The following labels for treatment will be used on all tabulations where the results are displayed by treatment or sequence, in the following order:

Part 1a:

- All Placebo
- ATH-399A 5 mg
- ATH-399A 10 mg
- ATH-399A 20 mg
- ATH-399A 40 mg
- ATH-399A 80 mg
- All ATH-399A

Part 1b:

- Treatment A (Fed)
- Treatment B (Fasted)

or

This document is confidential.

- Sequence AB
- Sequence BA

Part 2:

- All Placebo
- ATH-399A TBD mg
- ATH-399A TBD mg
- ATH-399A TBD mg
- All ATH-399A

6.2 Summary Statistics:

Unless otherwise stated, continuous variables will be summarized using the number of observations (n), and the statistics mean, median, standard deviation (SD), minimum (min) and maximum (max). The min and max values will be presented to the same number of decimal places as recorded in the eCRF, mean and median will be presented to one more decimal place than the raw data, and the SD will be presented to two more decimal places than the raw data.

Summaries of change from baseline variables will include only participants who have both a baseline value and corresponding value at the timepoint of interest. Categorical and binary variables will be summarized with frequency counts and percentages. Percentages will be rounded to one decimal place, with the denominator being the number of participants (N) in the relevant population, unless otherwise stated.

All digits will be used for PK and statistical calculations. For PK tables and listings, the final reportable results or data will be presented by rounding off to two decimal digits, except for the following situations (this applies to individual data and descriptive statistics):

- Terminal elimination rate constant (λ_z) data shall be rounded off to four decimal places.

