10.2 Adverse Events (AEs)

AEs will be coded using the latest version of the MedDRA. Output data will include the MedDRA version used in the study. AEs will be grouped by SOC and PT and summarized by actual treatment. The summary tables will present the number and percentage of total participants and number of events by SOC and by PT.

All AE summaries will be restricted to treatment-emergent AEs (TEAEs), defined as AEs that commence on or after the time of first study drug administration. Any AE that first occurs pre-dose but worsens in intensity after the first study drug administration will also be considered a TEAE. AEs without an onset date or time, or AEs with an onset date of the date of first study drug administration but without an onset time, will be defined as treatment-emergent, unless an incomplete date (e.g., month and year) clearly indicates that the event started prior to administration of first study drug, or the AE stop date indicates that the event started and stopped prior to administration of first study drug.

TEAEs will be attributed to the last treatment administered. TEAEs continuing after dosing in the next treatment period will be evaluated on a case-by-case basis.

The number and percentage of participants experiencing TEAEs and the number of TEAEs will be tabulated. Participants who experience the same TEAE (in terms of MedDRA PT) more than once will only be counted once per treatment or period, however, the total number of events will be counted per category. This also applies to sub-categories displayed in the summaries.

The following summaries will be presented:

- Overall summary of TEAEs
- TEAEs by SOC and PT
- TEAEs by SOC, PT, and intensity
- TEAEs by SOC, PT, and relationship to study drug
- Serious TEAEs by SOC and PT

The Investigator will make an assessment of intensity for each AE and SAE reported during the study per Common Terminology Criteria for Adverse Events (CTCAE) v5.0 grading criteria:

This document is confidential.

- Grade 1: Mild, asymptomatic or mild symptoms; clinical or diagnostic observations only; treatment not indicated.
- Grade 2: Moderate, minimal, local, or non-invasive treatment indicated; limiting age-appropriate instrumental activities of daily life.
- Grade 3: Severe or medically significant but not immediately life-threatening: hospitalization or prolongation of hospitalization indicated; disabling; limiting self-care activities of daily life.

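### Part 1a: only the 40 and 80 mg cohorts have contacts on Days 4 and 5, and the AE tables by dose neither show nor allow for this difference in ascertainment

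*SAP*

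**What the plan says.** **Contacts.** Table 1 of the protocol (Section 4.1) restricts the Day 4 and Day 5 outpatient columns to Cohorts 4 and 5. Protocol 7.1.1 gives their purpose: "PK blood samples for Cohorts 4 and 5 will be collected at outpatient visits on Day 4", with a second draw on Day 5. For those two days Table 1 marks PK blood but no vital signs, ECG, safety laboratory tests or examinations. Every cohort is discharged on Day 3 after the 48 h assessments, and every cohort returns once between Day 8 and Day 11.

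**AE collection.** Protocol 11.7.1 sets one window for everyone: "All AEs will be collected continuously from time of informed consent until the Follow-up Visit". Protocol 11.7.2 describes how events are found: "Open-ended and nonleading verbal questioning of the participant is the preferred method to inquire about AE occurrences".

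**Tabulation.** SAP 10.2 says that "AEs will be grouped by SOC and PT and summarized by actual treatment", giving both participants and events, with no split by time of onset. SAP 6.1 says that "all participants randomized to placebo will be pooled into a single placebo group". The Part 1a columns are therefore pooled placebo, the five doses, and all active doses combined. SAP section 10 plans no inferential analysis of safety.

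**The concern.** Overall AE incidence is among the primary endpoints of Part 1a (SAP 4.1.1). A single-ascending-dose AE table is read across its columns: each dose against placebo, and low doses against high. That reading assumes events had a similar chance of being recorded in each column. After discharge they may not have had. A mild event that starts and resolves within a few days is more likely to be mentioned the next day than up to a week later. Two further blood draws can also produce events of their own. Protocol 13.3.1 counts an untoward occurrence as an AE whether or not it is related to treatment, and SAP 10.2 counts anything starting after the first dose as treatment-emergent.

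Both routes act only at 40 and 80 mg and in the placebo participants of those two cohorts. A reader of the planned tables could take a step between 20 and 40 mg for a drug effect, and nothing in the SAP would warn against it.

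**Working it through.** **Inputs from the documents.** There are five cohorts of 8, each 6 active and 2 placebo: 5 × 8 = 40, the planned Part 1a size, made up of 30 active and 10 placebo. The documents give no AE rates and no reporting probabilities.

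**Contacts by column.**

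| | 5–20 mg | 40–80 mg | Pooled placebo |
|---|---|---|---|
| Scheduled contact days after dosing | 4 (Days 1, 2, 3, 8) | 6 (plus Days 4, 5) | 4 for six, 6 for four |
| Of these, after discharge | 1 | 3 | 1 for six, 3 for four |
| Participants with Day 4/5 visits | 0/18 | 12/12 | 4/10 |

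All active doses combined have 12/30 = 40% with the extra visits, and pooled placebo has 4/10 = 40%. That comparison is balanced. Only the columns for individual doses are affected.

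**Size for post-discharge events, no drug effect.** Assumptions: true post-discharge risk *r* = 0.20–0.40; capture *c*₁ = 0.60–0.80 with follow-up only; capture *c*₂ = 0.90–0.95 with the extra contacts. Reported incidence is *r* × *c*. Pooled placebo is 0.6 × low + 0.4 × high.

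| Case | 5–20 mg | Pooled placebo | 40–80 mg | High minus low | High minus placebo |
|---|---|---|---|---|---|
| Smallest: *r* = 0.20, *c*₁ = 0.80, *c*₂ = 0.90 | 16.0% | 16.8% | 18.0% | 2.0 | 1.2 |
| Largest: *r* = 0.40, *c*₁ = 0.60, *c*₂ = 0.95 | 24.0% | 29.6% | 38.0% | 14.0 | 8.4 |
| *c*₁ = *c*₂ | equal | equal | equal | 0 | 0 |

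**Size for overall incidence.** A participant already counted for an in-clinic event cannot be counted again. If 30–50% have an in-clinic TEAE, independently of later events (assumption), the step is multiplied by 0.5–0.7. The range becomes 2.0 × 0.5 = 1.0 to 14.0 × 0.7 = 9.8 points, or 12 × 0.010 = 0.1 to 12 × 0.098 = 1.2 expected extra participants among the 12 high-dose actives. One participant in a dose group of 6 is 16.7 points. This shrinkage does not apply to the event counts that SAP 10.2 also tabulates.

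**Cross-check with another model.** Let *p* be overall incidence on the common schedule, and *q* the chance that the extra contacts bring out an event in someone who would otherwise have none. The step is (1 − *p*)*q*. For *p* = 0.10–0.50 and *q* = 0.02–0.20 it runs from 0.5 × 0.02 = 1.0 to 0.9 × 0.20 = 18.0 points, and 0.6 times that against pooled placebo (0.6 to 10.8). At *p* = 0.30 and *q* = 0.10 the columns read 30.0%, 32.8% (placebo) and 37.0%, and the chance of at least one extra case among 12 is 1 − 0.93¹² = 0.58.

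**After the change.** With 40–80 mg set against the four placebo participants of Cohorts 4–5, and 5–20 mg against the six of Cohorts 1–3, both sides share a schedule. The expected schedule-driven difference is 0 for any *r*, *c*₁ and *c*₂.

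**The case against.** The strongest reply is that the observation period does not differ. Collection is continuous to the same Day 8–11 visit, so an event on Days 4 to 7 at 5–20 mg is still reportable at follow-up. The protocol schedules PK draws on Days 4 and 5 and does not say that a structured AE enquiry takes place there. Safety is descriptive, and TEAEs are also tabulated by intensity and relationship and listed by participant. Dose escalation rests on the Safety Review Committee's own criteria, not on this final table.

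Most of this stands. A reader might infer from the schedule that AE incidence must climb with dose by design, or that the whole dose trend is distorted. The documents support neither reading. Contacts are identical within 5–20 mg and between 40 and 80 mg, so no gradient can arise there. Scheduled laboratory, ECG and vital-sign findings cannot differ because of Days 4 and 5. The recall route needs mild events to be forgotten or left unmentioned by follow-up.

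Three things remain. A common window does not make the opportunity to report equal. Events caused by the extra draws do not depend on recall. And where no test is planned, the descriptive columns are the analysis.

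The texts also differ on how far Days 4 and 5 serve safety. SAP 3.3.1 ties dosing of the remaining participants in Cohorts 4 and 5 to 96 h of sentinel observation, while Protocol 7.1.1 gives 48 h for every cohort. These passages must be reconciled.

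It is also tempting to read the dose comparison from the first 48 h alone. That would take later-onset events out of the main comparison, including at the doses where PK sampling was extended to 96 h. The 48 h window is not fully protected either, because an early event may first be mentioned on Day 4 or 5.

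**Conclusion.** The point holds as a modest gap in the SAP. In Part 1a, the intensity of AE ascertainment after discharge differs between 5–20 mg and 40–80 mg, and the pooled placebo column mixes the two schedules. The possible artefact is one step between 20 and 40 mg: about 2 to 14 points for post-discharge events under the assumed risks and capture rates, smaller for overall incidence (about 1 to 10 points if 30–50% already have an in-clinic event), and zero if the extra contacts bring out nothing new. On these assumptions it amounts to roughly one participant or fewer among the 12 high-dose actives. None of the rates comes from the documents, so the direction is better supported than the size. The comparison of all active doses with all placebo is not affected.

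**What to change.** Keep the full-period TEAE tables as the main presentation. In SAP 10.2, for Part 1a:

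1. Add supplementary TEAE tables, overall and by SOC and PT, split by onset: up to 48 h post-dose, when scheduled contacts are the same in every cohort, and later.
2. In the later-onset table, show placebo separately for Cohorts 1–3 (n = 6) and Cohorts 4–5 (n = 4).
3. Add a footnote stating that only Cohorts 4 and 5 had visits on Days 4 and 5.
4. Where the report date is available, flag in the listing the AEs first reported at those visits. The documents do not say whether this date is recorded.

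Trial conduct and the planned assessments do not change. The cost is SAP wording and two extra table shells. The drawback is very small placebo columns, which allow a like-for-like reading but no precise comparison. Fixing the tables before unblinding avoids a post hoc explanation if a step between 20 and 40 mg appears.

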10.3 Laboratory Evaluations

Laboratory data, including hematology, biochemistry, coagulation, urinalysis, and thyroid panel, will be listed by participant and summarized for each visit/timepoint by treatment. Observed values and changes from baseline will be presented.

In addition, a shift table representing the categorical change (low, normal, high) from baseline to each post baseline visit/timepoint will be presented.

Abnormal results will be flagged in the listings.

If more than one clinical laboratory is used, a formula that takes into consideration the relative normal ranges of each test of the laboratories will be utilized to normalize these data.^d The conversion formula used for each test will depend on the typical distribution of the normal range for the test.^e Prior to applying these formulas, units will be adjusted, as necessary. The laboratory which has the most results for each parameter will be considered primary in the formulas.

10.4 Vital Signs

Vital sign measurements (temperature, blood pressure, pulse rate, and respiratory rate) will be listed by participant and summarized for each visit/timepoint by treatment. Observed values and changes from baseline will also be presented.

In addition, a shift table representing the categorical change (normal, abnormal not clinically significant, or abnormal clinically significant) from baseline to each post baseline timepoint will be presented.

This document is confidential.

Abnormal results will be flagged in the listings.

10.5 Electrocardiograms (ECGs)

Electrocardiogram (ECG) values (ventricular heart rate and the PR, RR, QRS, QT, and corrected QT interval using Fridericia's formula [QTcF] intervals) will be listed by participant and summarized for each visit/timepoint by treatment. Observed values and changes from baseline will be presented.

A shift table representing the categorical change in overall interpretation (normal, abnormal not clinically significant, or abnormal clinically significant) from baseline to each post baseline timepoint will be presented.

Abnormal results will be flagged in the listings.

A frequency table with a QTcF interval reading change from triplicate baseline (average) to any single QTcF interval reading greater than 20 ms, 40 ms, or 60 ms will be presented. Participants will only be counted once in each category.

10.6 12-Lead Telemetry

12-lead telemetry will be conducted for evaluation of cardiac arrhythmias. Abnormal results will be listed by participant.

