7.2 Justification for Dose

[REDACTED]

study progresses. The SRC recommendations should be based on results from a minimum of 6 evaluable participants in each dosing cohort.

Safety/tolerability data through the final follow-up visit for each of the 6 evaluable participants in a cohort along with PK data up to at least 48 hours post-dose in Part 1a and 1b (or 24 hours post-last dose in Part 2) will be assessed by the SRC prior to:

- a. Ascending from one dose-level cohort to the next higher dose level cohort in Parts 1a and 2,
- b. Prior to transitioning from Part 1a to Parts 1b and 2.

The SRC will stop dose escalation or descend to a dose level lower than the planned next higher dose level if any of the following criteria are met:

- One participant per cohort who receives ATH-399A experiences a serious adverse event (SAE) which is considered to be related to the study medication.
- Two participants per cohort who receive ATH-399A have QTc prolongation, defined as an average absolute (regardless of baseline value) QTcF >500 msec or an increase of QTcF > 60 msec above baseline, confirmed by repeating after 5 minutes, and determined post-dose.
- Two participants per cohort who receive ATH-399A exhibit hypotension, defined as resting supine diastolic blood pressure <40 mmHg persisting for at least 10 minutes on repeated assessment, or an asymptomatic or symptomatic fall in systolic blood pressure to below 80 mmHg, persisting for at least 10 minutes on repeated assessment.
- Two participants per cohort who receive ATH-399A exhibit hypertension, defined as an increase in resting systolic blood pressure to above 180 mmHg, persisting for at least 10 minutes, or an increase in resting diastolic blood pressure to above 105 mmHg, persisting for at least 10 minutes.
- Two participants per cohort who receive ATH-399A exhibit tachycardia, defined as resting supine heart rate >130 beats per minute, persisting for at least 10 minutes.
- Two participants per cohort who receive ATH-399A exhibit symptomatic bradycardia, defined as heart rate <40 beats per minute, or asymptomatic bradycardia, defined as resting supine heart rate <30 beats per minute while awake, persisting for at least 10 minutes, or clinically significant arrhythmia.
- One participant per cohort who receives ATH-399A exhibits abnormal liver tests defined as:
 - Aspartate aminotransferase (AST) or alanine aminotransferase (ALT) $>5X$ upper limit of normal (ULN).

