11.6.3 Electrocardiograms

12-Lead ECGs will be performed in triplicate, at least 1 minute apart, all within 10 minutes, and will be performed and interpreted according to the site's standard operating procedures. Average

values should be recorded. The ECGs will be performed after the participant has been resting in a supine position for at least 5 minutes. The ECG will electronically measure and calculate ventricular heart rate and the PR, RR, QRS, QT, and QTcF intervals. The QTcF interval will be used for clinical evaluations.

If a clinically significant abnormality is detected, the abnormality should be documented as an AE and followed until resolution with additional ECGs as medically indicated.

11.6.4 12-Lead Telemetry

12-Lead telemetry for evaluation of cardiac arrhythmias will be conducted at the time points noted in the SoAs.

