- PK parameters related to time, such as time of maximum observed concentration (T_{max}) must be reported with the same precision as the actual sampling time, rounded to three decimal places.
- Concentration versus time data, as well as maximum observed concentration (C_{max}) shall be reported as they appear in the corresponding dataset.
- Ratios and 90% CIs, intra- and inter-participant coefficients of variation (CV), and CV (%) will be presented to two decimal places.

Only data from protocol scheduled (“nominal”) visits will be included in the summary tables. Data from unscheduled visits will not be included in the summary tables (unless they were used as baseline) but will be included in the listings.

This document is confidential.

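### The QTcF category table in SAP 10.5 sets a triplicate-average baseline against any single post-dose reading, which raises chance counts at >20 ms and may not be producible if only averages are held

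*SAP*

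**What the plan says.** SAP 10.5 (Electrocardiograms) defines the only categorical QTcF display as "A frequency table with a QTcF interval reading change from triplicate baseline (average) to any single QTcF interval reading greater than 20 ms", with further cut-offs at 40 and 60 ms. It adds that "Participants will only be counted once in each category". Each row therefore counts participants whose highest post-dose reading, less baseline, passes the cut-off.

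Protocol 11.6.3 says that "12-Lead ECGs will be performed in triplicate, at least 1 minute apart, all within 10 minutes" and that average "values should be recorded". Neither document says whether the three individual readings are also kept in the database.

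The QTc criterion in the dose-escalation rules (Protocol 7.3 in the table of contents, repeated in the synopsis and in 10.1) reads "average absolute (regardless of baseline value) QTcF >500 msec or an increase of QTcF > 60 msec above baseline, confirmed by repeating", with the repeat due 5 minutes later. SAP 10.5 plans no category for absolute QTcF and none for confirmed increases.

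SAP 6.2 (Summary Statistics) adds a general rule: "Data from unscheduled visits will not be included in the summary tables", apart from values used as baseline. Such data still go into the listings.

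**The concern.** Triplicates are taken to reduce measurement noise. Averaging at baseline but not after dosing gives up that gain on one side. It also triples the number of chances each participant has to pass a cut-off, because all three readings at each time point count. ECG change is part of the primary safety endpoint in every part, and a dose column holds only six active participants, so a few chance counts can shape how the table reads.

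There are three related problems:

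- **Feasibility.** If only averages are captured, the table as worded cannot be programmed.
- **Reconciliation.** A reader of the study report cannot match the table to the Protocol's QTc criterion, because the >500 msec limb and the confirming repeat are absent.
- **Omitted readings.** Protocol 11.6.3 calls for further ECGs after a clinically significant abnormality. Any that are recorded as unscheduled visits would fall outside a table meant to capture a change at any time.

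**Working it through.** The plan gives no expected rate, variance or sample-size basis for this table, so there is no figure to reproduce. The check is how often a participant with no drug effect would be counted under each definition.

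**Inputs from the documents**

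- Three readings per time point (Protocol 11.6.3). Baseline is the last value before the first dose (SAP 6.3), which is one triplicate.
- Part 1a post-dose time points (Protocol Table 1, footnote 5): 1, 2, 4, 8, 12, 16, 24, 36 and 48 h, and follow-up = 10, or 30 single readings.
- Part 2 (Protocol Table 3, footnote 5): 6 on Day 1, 10 × 2 = 20 on Days 2–11, 5 on Day 12, 1 on Day 13 and 1 at follow-up = 33, or 99 single readings.
- Active participants: 5 × 6 = 30 in Part 1a and 3 × 6 = 18 in Part 2. Pooled placebo (SAP 6.1): 5 × 2 = 10 and 3 × 2 = 6.

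**Assumptions (not in the documents)**

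A reading is a time-point deviation (SD sb) plus a replicate error (SD sw). Both are normal and independent, with no drug effect and no diurnal trend. The range is sb 4–10 ms and sw 3–8 ms. Total single-reading SD = √(sb² + sw²), which is 5.0 to 12.8 ms.

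**One comparison**

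- Single reading minus mean baseline: variance = 2sb² + (4/3)sw².
- Mean minus mean: variance = 2sb² + (2/3)sw².
- With sb = 6 and sw = 5: 72 + 33.3 = 105.3 (SD 10.3 ms) against 72 + 16.7 = 88.7 (SD 9.4 ms). The chance of exceeding 20 ms is 2.6% against 1.7%.

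The table then takes the maximum over 30 or 99 single readings, instead of 10 or 33 means. All comparisons share one baseline, so the maximum was simulated with 100,000 participants per scenario.

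**Participants above 20 ms with no drug effect: single reading → mean**

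| Total SD (sb, sw), ms | Part 1a | Part 2 |
|---|---|---|
| 5.0 (4, 3) | 2.3% → 0.5% | 5.9% → 1.4% |
| 6.4 (5, 4) | 12.2% → 3.7% | 24.0% → 8.2% |
| 7.8 (6, 5) | 27.0% → 10.4% | 44.9% → 20.3% |
| 8.6 (7, 5) | 34.5% → 17.2% | 53.6% → 30.5% |
| 10.0 (8, 6) | 46.7% → 25.6% | 66.8% → 42.3% |
| 11.7 (10, 6) | 56.0% → 37.6% | 75.0% → 56.7% |
| 12.8 (10, 8) | 63.9% → 40.3% | 81.6% → 59.3% |

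- **Ratio.** The largest is 2.31/0.46 = 5.0 and the smallest is 74.96/56.74 = 1.3.
- **Counts at SD 7.8 ms.** Part 1a: 0.270 × 30 ≈ 8 active participants against 0.104 × 30 ≈ 3. Part 2: 0.449 × 18 ≈ 8 against 0.203 × 18 ≈ 4.
- **>40 ms row.** Below 0.4% on single readings up to SD 7.8 ms. At SD 12.8 ms it is 12.2% → 3.8% in Part 1a and 24.1% → 8.3% in Part 2.
- **>60 ms row.** At most 0.5% → 0.1% in Part 1a and 1.2% → 0.2% in Part 2.

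**The case against.** **The wording could mean any one time point.** If only averages are stored, a single reading could be read as one time-point value, and the comparison would already be mean against mean. The sentence itself contrasts a triplicate average with a single reading, so the literal sense is the likelier one. The eCRF and table shells would settle it and are not available. On either reading the sentence needs defining.

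**The size is assumed.** This stands. At an SD of 5 ms only 2.3% and 5.9% are counted above 20 ms. A reader might infer that the table will flag many participants by chance. The documents do not support that as a general statement, because they give no variance and the effect lies mainly in the >20 ms row, which triggers nothing in the Protocol.

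**Averaging is only part of the answer.** This also stands. At SD 7.8 ms, means still count 10% and 20%, because a maximum over 10 or 33 time points remains.

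**The SAP offers other safeguards.** Observed values and changes are summarised at every time point, values are listed with abnormal results flagged, and safety analysis is descriptive. Pooled placebo follows the same schedule and so has the same expected chance rate. That reference is small, though (10 and 6 participants), and Part 1b has none.

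**The >500 msec row is largely redundant.** QTcF above 450 msec at screening and Day -1 is exclusionary, so a value above 500 would usually mean a rise of more than 50 ms and already sit in the >40 ms row. That is fair, but such a value would not be visible there as meeting the Protocol's absolute limb.

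**Unscheduled ECGs.** A 5-minute repeat at a scheduled time point need not be recorded as an unscheduled visit. Adding symptom-driven ECGs also gives some participants more chances to be counted. Both are fair limits on this part of the point.

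**Conclusion.** The mismatch is in the text and needs no simulation: an averaged baseline is set against single readings, in a protocol that has averages recorded. Single readings raised the chance count at >20 ms in every scenario, by about 1.3 to 5 times. The absolute rates rest on assumed variances and on independent time-point deviations. The >60 ms row, the only one that shares a cut-off with the Protocol, is nearly unaffected.

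Two stronger readings should be resisted. First, it is tempting to say that the table contradicts averages on which the Protocol stops escalation. The word 'average' is attached only to the >500 msec limb; the >60 msec limb asks for confirmation by repeat and does not say average. Second, the table does not distort escalation decisions. It belongs to the final analysis, while SAP 1.2 gives the Safety Review Committee blinded data extracts during the study.

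This is a cheap improvement to a descriptive table. It does not threaten the trial's conclusions.

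**What to change.** Amend SAP 10.5 and the table shell:

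1. Define the post-dose value as the mean of the triplicate at each time point, compared with the mean of the pre-dose triplicate, for >20, >40 and >60 ms.
2. Add a >500 msec row on the same averages, so that the table reflects the Protocol's existing criterion. The criterion itself does not change.
3. Count unscheduled post-dose ECGs in this table, as a stated exception to SAP 6.2.
4. Confirm which readings the eCRF holds. If single readings are kept, show their maxima in the listing or in a second panel.

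The cost is SAP wording and one table shell, with no change to data collection. There are two downsides. An isolated high reading is diluted in the main table, which the listing or second panel offsets. Unscheduled ECGs give some participants more chances to be counted, which a footnote should state.
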